In order to expedite the study of the safety of mRNA-1273 in school-aged children 6 years to < 12 years of age; Part 1 will enroll a total of approximately 375 participants per dose (both at the 50 and 100 µg dose levels) in this age group (6 years to < 12 years). The first 75 of these participants per dose will be included in the safety evaluation for dose-escalation and age de-escalation as well as the immunogenicity assessment needed for dose selection, as applicable. Additionally, approximately 300 participants per dose will be enrolled to assess for any AE occurring at 1% or higher. The sample size for Part 2 in this age group (6 years to < 12 years) will be adjusted to approximately 1700 participants. Conversely, approximately 75 participants in the middle age group (2 years to < 6 years) will be enrolled per dose in Part 1 for safety and dose selection and Part 2 will utilize the dose selected in Part 1 to inform on AEs occurring at a frequency of 1% or greater. In the youngest age group (6 months to < 2 years), approximately 150 participants will be enrolled per dose in Part 1 for safety and dose selection and Part 2 will utilize the dose selected in Part 1 to inform on AEs occurring at a frequency of 1% or greater. For details, please refer to [Section 7.5](#).

The study will begin with the oldest age group (6 years to < 12 years) and age de-escalate as described under Study Progression. Each age group will begin with Part 1 and may advance to Part 2 and Part 3 independently. For details, please refer to the study schematic in [Figure 1](#).

The mRNA-1273 investigational vaccine or placebo will be administered as 2 IM injections approximately 28 days apart for Part 1 and Part 2. For Part 3, the mRNA-1273 investigational vaccine will be administered as 3 IM injections approximately 28 days apart for the 2 doses of primary series followed by a third dose at least 3 months and up to 5 months after receipt of the second dose of the primary series. The mRNA-1273 dose levels that will be evaluated in each age group in Part 1, Part 2 and Part 3 of the study are given in [Table 3](#).

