### 5.2 Randomization

Random assignment of participants in Part 2 of the study will use a centralized interactive response technology, in accordance with pregenerated randomization schedules. Up to 4,000 participants each in the 6 years to < 12 years, 2 years to < 6 years, and 6 months to < 2 years age groups will be randomized in a 3:1 ratio to the mRNA-1273 arm (n = up to 3,000 participants in each group) or placebo arm (n = up to 1,000 participants in each group).

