## 7.2 Blood Collections for Immunogenicity Assessments and Biomarker Samples

Blood samples for immunogenicity assessments and biomarker samples will be collected at the time points indicated in the SoAs ([Section 10.1](#)). The following analytes will be measured:

- Serum nAb titer against SARS-CoV-2 as measured by pseudovirus and/or live virus neutralization assays.
- Serum bAb titer as measured by enzyme-linked immunosorbent assay specific to the SARS-CoV-2 S protein.
- For Part 1, testing for serologic markers for SARS-CoV-2 infection using a nonvaccine antigen-based blood test at Day 1 (prior to the first dose), Day 57, Day 209, and Day 394.

For Part 2, participants in each age group will be assigned to 5 phlebotomy cohorts. Blood sampling will be performed in 3 of these 5 cohorts for immunogenicity at 3 of the following time points: Day 1 (prior to randomization and the first dose), Day 57, and one of Day 29 (prior to the second dose), Day 209, and Day 394. Participants in the Cohort D (remainder of the age group) will provide a blood sample at Day 1 (prior to randomization and the first dose) and within 4 days of receiving Dose 2 at Day 30 (+3 days) for storage and potential future biomarker testing (may include cardiac biomarkers). For participants already enrolled in Cohort D prior to Amendment 4, this blood draw will be optional and confirmed at time of re-consenting; for all participants newly enrolled into Cohort D under Amendment 4, it will be mandatory. A fifth cohort of participants at selected VTEU sites only, will provide blood samples for assessment of exploratory serology and CMI on Day 1 (prior to randomization and the first dose), Day 43, Day 209, and Day 394.

All participants in Part 3 of the study will provide blood specimens for immunogenicity on Day 1 (prior to the first dose) and will also provide additional samples at Day 57, Day 149/BD-Day 1, one month after the third dose on Day 177/ BD-Day 29. The first 150 participants (Sub-Cohort F) will also have a blood draw on Day 329/BD-Day 181; the second 150 participants (Sub-Cohort G) will also have a blood draw on Day 514/BD-Day 366.

All participants in Part 1 and Part 2 who choose to receive a booster dose will provide a blood specimen for immunogenicity and serostatus on BD-Day 1; a subgroup of participants will also provide one additional blood specimen for immunogenicity. Please see [Table 16](#) for details.

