**Table 10: Analysis Sets**

Analysis Set	Description
Randomization Set	Part 2: All participants who are randomly assigned, regardless of the participants' treatment status in the study.
Full Analysis Set (FAS)	Part 1: All enrolled participants in Part 1 who receive at least 1 injection of IP. Part 2: All randomly assigned participants who receive at least 1 injection of IP. Part 3: All enrolled participants in Part 3 who receive at least 1 injection of IP.
Per Protocol (PP) Set	All participants in the FAS who receive planned doses of IP per schedule, comply with the immunogenicity schedule, and have no major protocol deviations that impact key or critical data. Participants who are RT-PCR positive or seropositive at baseline will be excluded from the PP Set. The PP Set in Part 1 will be used for all analyses of immunogenicity in Part 1 unless specified otherwise.
Immunogenicity Subset	A subset of participants in the FAS will be selected for immunogenicity sampling and testing.
Per Protocol Immunogenicity Subset	A subset of participants in the FAS will be selected for immunogenicity testing. The PP Immunogenicity Subset includes participants selected for the Immunogenicity Subset who receive planned doses of IP per schedule, comply with immunogenicity testing schedule, and have no major protocol deviations that impact key or critical data. Participants who are RT-PCR positive or seropositive at baseline will be excluded from the PP Immunogenicity Subset, in addition to participants with HIV who are receiving highly active anti-retroviral therapy (HAART). The PP Immunogenicity Subset will be used for all analyses of immunogenicity unless specified otherwise.
Safety Set	All enrolled participants (in Part 1 and Part 3) and all randomly assigned participants (in Part 2) who receive at least 1 dose of IP. The Safety Set will be used for all analyses of safety except for solicited ARs. Safety Set for the booster/third dose phase will include all participants who receive a booster dose or third dose.
Solicited Safety Set	The Solicited Safety Set consists of participants in the Safety Set who contributed any solicited AR data. The Solicited Safety Set will be used for the analyses of solicited ARs.

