#### **8.5.4 Efficacy Analysis**

To evaluate the incidence of COVID-19 after vaccination with mRNA-1273 or placebo, the incidence rate will be provided by vaccination group, dose level, and age group, calculated as the number of cases divided by the total person-time. Participants in Part 1 and Part 2 of the study and in different age groups who receive the same mRNA-1273 dose level (if applicable) may be combined in the analysis.

For serologically confirmed SARS-CoV-2 infection or COVID-19, regardless of symptomatology or severity, infection rate will be provided by vaccination group, dose level, and age group. The same analysis will be conducted for asymptomatic SARS-CoV-2 infection.

The secondary efficacy analyses will be performed on the PP Set, with sensitivity analyses in FAS, modified Intent-to-Treat (mITT) Set, and modified Intent-to-Treat-1 (mITT1) Set. Analyses of the efficacy endpoints in Part 2 will be performed for the randomized blinded phase. Additional exploratory analyses will be conducted in the blinded and unblinded phases for participants randomized to mRNA-1273 in Part 2, and in the unblinded phase for participants who are originally randomized to the placebo arm and cross-over to mRNA-1273 after use of any COVID-19 vaccine is authorized or licensed for the participant's age group.

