- Participant unblinds and has received placebo:
  - Participant will have 2 options:

1. Discontinue participating in the KidCOVE study
2. Cross-over to mRNA-1273 (following [Table 13](#)- through Day 57 safety follow-up call)
  - A pregnancy test should be done for participants that are post-menarche prior to Dose 1 and Dose 2.
  - For the remainder of the study visits, as noted in [Table 13](#), the participants will be followed for MAAEs, SAEs, and AESIs and concomitant medication relevant to, or for the treatment of MAAEs and SAEs.
  - Participants will continue being followed for safety, which includes COVID-19 surveillance, using electronic eDiaries and safety follow-up calls that will continue to trigger from the participant's original (placebo) administration date.
  - Participants will have a clinic visit at study Day 209 from the original (placebo) administration date. At this visit, they will have a symptom-directed physical exam, if necessary, illness visit or convalescent visit work-up, if applicable, and a nasal swab. No blood samples will be required for this visit.
  - Participants will have a clinic visit at study Day 394 from the original (placebo) administration date. At this visit, they will have a symptom-directed physical exam, if necessary, illness visit or convalescent visit work-up, if applicable, and a nasal swab.

In summary: No immunogenicity or serology samples will be required for cross-over participants unless they are part of a convalescent visit work-up or if they choose to receive a booster dose (as per [Table 15](#), they will require a BD-Day1 baseline blood draw.)

**Table 14: Phlebotomy Schedule for Serology, Biomarker Sample, and Cell-Mediated Immunity for Part 2 (Expansion) of the Study**

**For participants that chose to receive a booster dose under protocol Amendment 7, please see [Table 16](#) for the booster dose phlebotomy schedule.**

**If Day 209/Day 394 blood draw is within 30 days of planned BD-Day 1, BD-Day 1 blood draw can be used for Day 209/Day 394.**

Cohort	Number of Subjects		Study Visit Day					
		D1 	D29 	D30 (+3) 	D43	D57	D209 (+30 days) 	D394 (+30 days) 
Phlebotomy Schedule for Serology: To be Executed Within Age Group								
A	First 176 (132 mRNA-1273: 44 placebo)	X	X			X		
B	Next 176 (132 mRNA-1273: 44 placebo)	X				X	X	
C	Next 176 (132 mRNA-1273: 44 placebo)	X				X		X
D	Remainder of the age group	X		X 				

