Phlebotomy Schedule for Cell-Mediated Immunity: To be Executed Within Each Age Group at Selected VTEU Sites only								
E (CMI with exploratory serology)	24 (18 mRNA-1273: 6 placebo)	X			X		X	X

Abbreviations: BD = booster dose; CMI = cell-mediated immunity; D = day; mRNA = messenger RNA; VTEU = Vaccine and Treatment Evaluation Units.

. On Day 1, sample must be collected prior to randomization and dosing. On Day 29, sample must be collected prior to dosing.

. If a Day 1 (baseline) blood sample cannot be obtained in either Part 1 or Part 2, the participant will be considered either a screen failure due to inability to satisfy inclusion criterion 3 or could be scheduled for rescreening. Participants may be rescreened 1 time, either within same screening period for Part 1 or Part 2 or in a new screening period for Part 2 if the initial screening was in Part 1. If the participant is rescreened and a blood sample still cannot be obtained, then he/she will be considered a screen failure due to inability to satisfy inclusion criterion 3.

. Serum sample from ~4 ml of blood only, to be stored for potential future use for biomarker assessment.

. If the participant decides to receive a booster dose, the BD1 blood draw ([Table 15](#)) can be used for Day 209 or Day 394 ([Table 14](#)).

**Table 15: Schedule of Assessments for Optional Booster Doses with mRNA-1273 for Parts 1 and 2, Study Arms 1 Through 9 under Protocol Amendment 7**

Visit Number	BD-1	BD-2	BD-2A	BD-3			BD-4	BD-5	BD-6
Type of Visit	C	SC	C	C	SFU		C	SC	C
Study Visit Day	BD-D1 	7 days after BD-D1 (BD-D8)	14 days after BD-D1 (Sub-Cohort E only and optional) BD-D15	BD-D29	eDiary	SC			
Window Allowance (Days)	0	+ 3	+ 3	-3/+14	± 3	± 3	-3/+14	+ 3	-3/+14
Days Since Most Recent Vaccination	0	7	14	28			180	270	365
Confirm informed consent /assent form booster addendum signing	X								
Physical examination 	X			X			X		X
Pregnancy testing 	X								
Immunogenicity Assessment									
Pre-booster blood for immunologic analysis  (or CMI with exploratory serology, as applicable) 	X								
Post-booster blood for immunologic analysis (or CMI with exploratory serology, as applicable) 			X	X			X		X
Dosing									
Study injection (including 30-minute post-dosing observation period) 	X								
Unscheduled Visits 	X	X	X	X	X	X	X	X	X
Nasal swab 	X			X			X		

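### Section 8.5.4 assigns serology-based and asymptomatic infection rates to analysis sets in which about 86% of a full Part 2 age group has no scheduled post-baseline serology, so absolute rates and rate differences are understated

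*Protocol*

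**What the plan says.** Protocol Section 7.3.1 and Table 2 define infection, in children negative at baseline, as anti-nucleocapsid seroconversion after Day 1 or a positive RT-PCR after baseline. Asymptomatic infection uses the same two markers in the absence of symptoms.

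Section 8.5.4 then says: "For serologically confirmed SARS-CoV-2 infection or COVID-19, regardless of symptomatology or severity, infection rate will be provided by vaccination group, dose level, and age" group. Asymptomatic infection gets the same analysis. On the analysis set: "The secondary efficacy analyses will be performed on the PP Set". FAS, mITT and mITT1 serve as sensitivity sets, and Part 2 is analysed for the randomized blinded phase. Table 10 draws all four sets from the whole FAS. None is limited to children with a post-baseline anti-nucleocapsid result.

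Table 14 fixes who is bled. Cohort A is "First 176 (132 mRNA-1273: 44 placebo"), and Cohorts B and C are the next two blocks of the same size. Cohort E has 24 children with exploratory serology. Everyone else is Cohort D. Section 7.2 says of them: "Participants in the Cohort D (remainder of the age group) will provide a blood sample at Day 1 (prior to randomization and the first dose"), plus one draw at Day 30 (+3 days). Table 14, footnote 3, says that this serum is "to be stored for potential future use for biomarker assessment".

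**The concern.** The endpoint has a serological limb and an RT-PCR limb, but for most of the stated denominator only the RT-PCR limb can operate. A Cohort D child who seroconverts without a positive swab cannot become a case through any scheduled primary-series test, yet belongs to every set that Section 8.5.4 names. Two ascertainment methods are therefore combined under one definition, and the reported rate depends partly on how many children were scheduled for serology.

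At stake are two secondary endpoints: infection overall and asymptomatic infection. Section 3.1 says that infection incidence will be compared between vaccine and placebo recipients. The absolute rates, and any difference between them, would be too low. The three sensitivity sets would not reveal this, because each contains Cohort D as well.

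**Working it through.** **Inputs.** Cohort sizes and draw days: Table 14. Part 2 size: Section 5.2 ("Up to 4,000 participants each in the 6 years to < 12 years, 2 years to < 6 years", and likewise the youngest group, randomized 3:1). Section 3.1 has a conflicting figure for the oldest group ("will be adjusted to approximately 1700 participants"), used here as a sensitivity case. Swab days: Section 3.1.1.2.

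**1. The plan's own figure.** A + B + C = 3 × 176 = 528, of whom 3 × 132 = 396 receive mRNA-1273 and 3 × 44 = 132 placebo. This matches the Immunogenicity Subset in Section 8.3. Adding E (18 + 6 = 24) gives 552, or 414 and 138 by arm.

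**2. Share without scheduled post-baseline serology.**
- N = 4,000: 4,000 − 552 = 3,448, or 86.2%.
- By arm: (3,000 − 414)/3,000 = 2,586/3,000 = 86.2%, and (1,000 − 138)/1,000 = 862/1,000 = 86.2%.
- If Cohort E's exploratory serology does not count: (4,000 − 528)/4,000 = 86.8%.
- N = 1,700: (1,700 − 552)/1,700 = 1,148/1,700 = 67.5%.

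**3. Coverage by visit (N = 4,000).** Day 57: 528/4,000 = 13.2%. Day 209: (176 + 24)/4,000 = 5.0%. Day 394: likewise 5.0%. No scheduled serology after Day 57: 1 − (176 + 176 + 24)/4,000 = 90.6%.

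**4. RT-PCR coverage of Cohort D.** Scheduled swabs fall on Days 1, 29, 57, 209 and 394, leaving gaps of 209 − 57 = 152 and 394 − 209 = 185 days. Within these gaps, detection depends on illness visits and, for asymptomatic children, household-exposure visits (Section 7.1.5).

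**5. Size of the understatement.** Let f be the share with scheduled serology and s the fraction of infections that RT-PCR alone detects, relative to RT-PCR plus serology. Then

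observed/true = k = f + (1 − f) × s,

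with f = 552/4,000 = 0.138 or 552/1,700 = 0.325. The value of s is an assumption. Setting s = 0 describes the purely serological component.

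| s | k, N = 4,000 | A true 10% would read | k, N = 1,700 |
|---|---|---|---|
| 0 | 0.14 | 1.4% | 0.32 |
| 0.25 | 0.35 | 3.5% | 0.49 |
| 0.50 | 0.57 | 5.7% | 0.66 |
| 0.75 | 0.78 | 7.8% | 0.83 |

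The formula treats all 552 as fully ascertained. Cohort A has no serology after Day 57, and B and C have one later draw each. The formula also assumes equal true incidence in Cohort D and the serology cohorts.

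**6. Effect on the comparison.** With the same f in both arms (step 2), and s taken as equal, true rates I₁ (vaccine) and I₀ (placebo) are observed as k·I₁ and k·I₀. The ratio is unchanged. The difference shrinks to k·(I₀ − I₁).

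**The case against.** The strongest reply is that the protocol only promises an infection rate. It gives no evaluability or censoring rule for these endpoints, and Section 8 leaves detail to the SAP, which is not at hand and could restrict the denominator. It is indeed an inference that a Cohort D child without a serology result counts as uninfected. But the protocol does more than stay silent: it names four sets for these rates, and each includes Cohort D without condition. The point stands for the plan as written.

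Four stronger readings are tempting, and the documents do not support them.

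- **That a scheduled swab is the only way to find an asymptomatic infection in Cohort D.** Section 7.1.5 also arranges a visit for asymptomatic children about 7 days after COVID-19 is diagnosed in the household, and asks for PCR confirmation or a site visit after a positive home test. Neither is limited by cohort.
- **That the understatement has a known size.** No document gives s, so only a range can be shown.
- **That the vaccine/placebo comparison is badly biased.** Every serology cohort is allocated 3:1, so Cohort D is the same planned share of each arm.
- **That the PP Set definition should change too.** Table 10 asks that children "comply with the immunogenicity schedule, and have no major protocol deviations that impact key or critical data". Cohort D can comply with its own schedule, so the clause does not remove it. FAS, mITT and mITT1 carry no such clause and already serve as sensitivity sets. Preferring a different PP definition is a matter of choice and is not part of this point.

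Later blood does not close the gap. Section 10.2.10 allows exploratory antibody work on stored Cohort D serum, but the Day 30 sample could cover only the first month. The BD-Day 1 serostatus draw depends on choosing a booster and falls largely outside the blinded phase.

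**Conclusion.** The concern holds in this form: Section 8.5.4 assigns serologically confirmed and asymptomatic infection to sets in which 86% of a full Part 2 age group (about 68% at 1,700) can be found infected only by RT-PCR. Absolute rates and rate differences are understated. The direction follows from the schedule; the size cannot be fixed from the documents. Observed over true is about 0.14 for the purely serological component in a group of 4,000, and about 0.35 to 0.78 for the combined endpoint under an assumed s of 25% to 75%.

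These figures assume that Cohort D stays in the denominator and that the 552 are fully ascertained. The approximate preservation of the ratio further assumes equal s in the two arms and an analysis kept within Part 2. Pooling with Part 1, which Section 8.5.4 allows for COVID-19 incidence, would break the balance if applied here, because Part 1 has no placebo arm and a different serology schedule.

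The endpoints are secondary and outside the multiplicity sequence, so no primary conclusion is affected. The published infection rates would nevertheless mislead.

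**What to change.** In Section 8.5.4:

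- Estimate serology-based infection and asymptomatic infection (RT-PCR and/or serology) in participants with at least one post-baseline anti-nucleocapsid result. End each child's follow-up at the last such result, which also deals with the different final draws in Cohorts A, B and C.
- Report RT-PCR-confirmed infection separately in all Part 2 participants.

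No new data are needed, and the PP Set definition can stay. The cost is precision. The serology-based rates would rest on at most 552 of 4,000 children (414 of 3,000 vaccine, 138 of 1,000 placebo) before PP exclusions. At the same underlying rate and follow-up, confidence intervals would be about √(4,000/552) = 2.7 times as wide as with full serology in everyone. Because Table 14 fills Cohorts A to C first, these rates would also describe mainly the earlier enrollees, and the report should say so.

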#### **8.5.5 Exploratory Analyses**

Exploratory analyses will be described in the SAP before database lock.

### **8.5.6 Subgroup Analyses**

Subgroup analyses will be performed as described in the SAP.

## **8.6 Study Analyses**

### **8.6.1 Interim Analyses**

Part 1: Interim analyses may be performed after all or a subset of participants (with immunogenicity samples collected for D1 and D57) have completed Day 57 within an age group in Part 1 (one optional interim analysis for each age group, 3 interim analyses total for the 3 age groups in Part 1). Analyses of safety and immunogenicity may be conducted at each interim analysis.

Part 2: An interim analysis of immunogenicity and safety will be performed after all or a subset of participants have completed Day 57 (1 month after the second dose) in Part 1 or Part 2 within an age group. This interim analysis will be considered the primary analysis of immunogenicity for a given age group. Another interim analysis on safety may be performed after a different subset or all participants have completed Day 57 in an age group. Additional interim analysis of immunogenicity and safety may be performed after all or subset of participants who receive booster dose have completed BD-Day 29 after the booster dose in an age group.

Part 3: An interim analysis of immunogenicity and safety will be performed after all or a subset of participants have completed Day 57 (1 month after the second dose) in Part 3 within an age group. This interim analysis will be considered the primary analysis of immunogenicity for the primary series in a given age group. A second interim analysis of immunogenicity and safety will be performed after all or a subset of participants have completed Day 177/BD-Day 29 (1 month after third dose).

An interim analysis of safety for mRNA-1273.214 booster may be performed after all or subset of mRNA-1273.214 recipients have completed 6 months of follow-up after the booster dose.

